Microfidelity (MIFI) Ablation Technology versus Standard Ablation Catheter for
Atrioventricular Nodal Ablation

A Comparative Pilot Study of Time to Success

Principal Investigator: [name]

Co-investigators: [name] MD

Introduction

In some elderly patients with atrial fibrillation (AF), especially in combination with heart failure, a rate control strategy may be preferred. When pharmacological therapy is ineffective or not tolerated, it is reasonable to perform atrioventricular (AV) node ablation with ventricular pacing as a class IIA indication per current guidelines [1].

Usually, the procedure is simple and straightforward and complete heart block can be achieved without any difficulty. However, this “simple” procedure can sometimes prove to be a most difficult case. The most common reason for failure to achieve complete heart block is the inability to localize the compact AV node using the His signal with standard intracardiac electrograms. As these patients come to the laboratory in AF, the His signal may be obscured by AF waves. In some patients with a deeper intramyocardial location of the His bundle and compact AV node it becomes necessary to produce deeper ablation lesions using an irrigated catheter to achieve block.

In patients with AF, the target of ablation for the “ablate and pace” approach is the compact AV node, located at the apex of the triangle of Koch. Ideally, ablation is performed at the most proximal penetrating part of the His bundle in order to maintain a proximal automatic junctional rhythm and avoid pacemaker dependence.

Para Hisian pacing is most commonly used to reveal the presence of a septal accessory pathway.

[2-3]

The His bundle is a deep insulated structure and it is difficult to capture it at usual energy outputs. Using a high- output pacing (usually 20 mA at 2 msec) it is possible to directly capture the deeply situated His bundle, which is confirmed by a narrower QRS complex on the paced electrograms. Thus, high-output pacing can be utilized to map the His bundle area in difficult situations.

By applying this electrophysiologic principle of differential tissue capture to help identify the location of the compact AV node, which is in close proximity to the His bundle. Ventricular pacing was performed initially at high output to capture both the basal right ventricular myocardium and the His bundle and the output was gradually lowered to lose His bundle capture. The QRS duration is relatively narrow with high output pacing and increases when the pacing output is lowered, representing ventricular myocardial capture alone. Finally, loss of ventricular capture is seen with further reduction of pacing output. This maneuver has been shown to aid in determining the proximity of the ablation catheter to compact AV node as was validated by successful ablation at this site. Parahisian pacing in conjunction with av nodal ablation has recently been described in the literature [4-5].

A novel catheter with three mini electrodes within the ablation tip (IntellaTip MiFi, Boston Scientific, Boston, MA) may enhance the available data for such a signal dependent technique. In this catheter, bipolar signals can be recorded between the three 0.8-mm-wide electrodes that

are arranged radially 1.3 mm from the end of the catheter alongside the standard distal and proximal bipolar recordings. Animal studies have already demonstrated that the mini electrodes in this novel catheter are more accurate in identifying conducting gaps in linear ablations than conventional electrode recordings [6].

Study Aims:

The aim of our study is to investigate the comparative efficacy of high fidelity multi electrode ablation catheters vs the standard bipolar configuration in success of AV nodal ablation. Both catheters are FDA approved and are being used as indicated on its label. For the purpose of this study, the standard bipolar catheter will be 8mm non-irrigated, and from the following list: Boston Scientific Blazer, Biosense Thermocool Non-Nav, and the St. Jude Sapphire. All of these catheters are currently used in ablation cases at the study site. This study will provide insights on the use of new technology where application may increase efficacy, promote patient and physician safety and decrease costs.

Primary and secondary objectives

Primary endpoints

1. Acute success of ablation identified by a junctional rhythm or complete heart block
2. Time from application of radiofrequency energy to acute success

Secondary endpoints include

1. Procedure time
2. Radiation time

3. Frequency of ablation application
4. Duration of ablation application

Research Plan

Inclusion Criterion

1. Patients with a diagnosis of **persistent or permanent atrial fibrillation** documented on electrocardiography
2. Patients must meet ACC/HRS guidelines for atrioventricular nodal ablation procedure
3. Patients have already been scheduled for their standard of care ablation
4. Patients must be available for at least 1 month post procedure
5. Patients must be greater than or equal to 18 years old.

Exclusion Criterion

1. Patients who do not meet ACC/HRS indications for av nodal ablation
2. Women who are pregnant

Research Design

The study will be performed at the University of Florida Health Science Center at UF Health, Jacksonville-Division of Cardiology. Patients will be recruited in the Cardiology Clinics of our institution and will be screened by Cardiology Research Staff, who will verify all
NCT03114124 1/25/2021

candidates meet inclusion and exclusion criteria.

Patients found eligible, n=30 for this study will already have a diagnosis of atrial fibrillation and be indicated for an ablation per standard of care. After providing written informed consent, subjects will be randomized by random computer programming to receive an ablation with MIFI technology or standard ablation catheter for their procedure. Data will be collected prospectively (perioperatively and at follow up visit).

During the ablation each patient will have a 3D electroanatomical map of the his bundle region created in addition to pacing along the region of interest. The target will be where the HIS electrogram amplitude is greatest and where the QRS complex from pacing is narrowest. Data will be collected until the primary endpoint of success is achieved.

Subjects will return to UF Shands -Jacksonville on day 30(+/- 14 days) to assess underlying conduction. If conduction has returned they will be offered an additional av nodal ablation per standard of care. If they undergo additional ablation this data will be included

Statistics

Sample Size Justification

This is a pilot study in which the primary aim is to estimate the time until successful end point in each of the two study arms. Thirty patients will be randomized (15 in each study arm). Variable block sizes will be used to improve the blinding of the clinical team. This information will then be used to design a fully-powered randomized study to compare these two arms. Patients will be randomly assigned to study arms. The project biostatistician and team will generate a set of envelopes which contain the random assignments for each patient. Once a patient has consented to participate, the next envelope will be opened for that patient and the catheter assignment will be revealed. This will maintain the blinding of NCT03114124 1/25/2021

the clinical team.

Statistical Analyses

The baseline demographic and clinical characteristics of the patients included in this study will be summarized by study arms. Frequencies and percentages will be summarized for categorical variables and means, standard deviations, medians, minima, and maxima will be summarized for numeric variables. For ordinal variables, the medians, minima, and maxima will be summarized. Based on the descriptive summaries and graphical summaries (e.g. box-and-whiskers plots), if there are individual baseline characteristics that differ between the study arms, these characteristics will be included a regression analysis to reduce the estimated variance of the difference between the study arms.

The primary analysis is the estimation of Kaplan-Meier median times to successful endpoints for each of the two study arms. Time zero is when the ablation procedure begins and the successful outcomes are either complete heart block or junctional rhythm. Patients in whom a successful endpoint is not reached will be censored at the time the procedure is stopped. A log-rank test will also be performed to compare these groups. If there are baseline characteristics that differ between the study arms based on the summaries described above, a Cox proportional hazards model will be fit that includes these baseline characteristics to adjust for these baseline differences in the study arms.

Additional Information

Subjects will be identified with a number and data collection sheets which will be stored in limited access areas, locked filing cabinets, and or in computers with security passwords. Data will be kept for 6 years after study completion to comply with UF and HIPAA regulations. Subjects will receive a hand out with names and phone numbers of the physicians and coordinators involved with the study.

Possible Discomforts and Risks

NCT03114124 1/25/2021

The most common risks associated with the procedure are per standard of care and include but are not limited to cardiac perforation, tamponade, vascular injury and pain. Possible serious adverse events may include cardiac tamponade, perforation and or death

Adverse Event

An adverse event is any unintended or undesirable experience that occurs during the course of the clinical investigation whether or not it is considered to be therapy related. This includes any newly occurring event or previous condition that has increased in severity or frequency since the initiation of study treatment. Adverse events will be followed until resolution while the patient remains on-study. Once the patient is removed from study, events thought to be related to the study therapy will be followed until resolution.

Serious Adverse Event

Serious Adverse Events (SAE): An adverse event occurring while on study and considered related (reasonable possibility that the study treatment caused the adverse experience) to the study treatment that results in any of the following outcomes:

- Death
- A life-threatening adverse experience.
- A persistent or significant disability, incapacity, or is a congenital anomaly, or birth defect.
- Requires inpatient hospitalization, or prolongation of existing hospitalization.

The definition of serious adverse event also includes ‘important medical event’. Medical and scientific judgment should be exercised in deciding whether expedited reporting is appropriate in other situations, such as important medical events that may not be immediately life-threatening

or result in death or hospitalization but may jeopardize the patient and/or may require medical or surgical intervention to prevent one of the other outcomes listed in the definition above. These should also usually be considered serious. Example of such event is an intensive treatment in an emergency room.

Serious adverse events will be reported per Boston Scientific and UF policy & procedure.

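### Acute success need only be reached, not held to the end of the procedure, and the day-30 conduction result feeds no listed endpoint or analysis

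*Combined protocol and SAP*

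**What the plan says.** The first primary endpoint (Primary and secondary objectives) is "Acute success of ablation identified by a junctional rhythm or complete heart block". The second is the time from radiofrequency application to that success.

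Statistical Analyses uses the same event: "the successful outcomes are either complete heart block or junctional rhythm". Its censoring rule is "Patients in whom a successful endpoint is not reached will be censored at the time the procedure is stopped". The main output is described thus: "The primary analysis is the estimation of Kaplan-Meier median times to successful endpoints for each of the two study arms". Sample Size Justification adds that the results will be used to design a fully powered trial.

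On recording, the Research Design paragraph about the ablation itself ends: "Data will be collected until the primary endpoint of success is achieved".

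On follow-up, the same section says: "Subjects will return to UF Shands -Jacksonville on day 30(+/- 14 days) to assess underlying conduction". Patients whose conduction has returned are offered another ablation, and then "If they undergo additional ablation this data will be included". The four listed secondary endpoints are procedure time, radiation time, and the frequency and duration of ablation applications.

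**The concern.** The event needs only to occur. Nothing requires the rhythm to be present when the procedure ends, and nothing covers a rhythm that is reached and then lost. A patient can therefore leave the laboratory conducting and still be scored as an acute success, with a short time. The stated aim is comparative efficacy in the success of AV nodal ablation, so that score does not match what the trial wants to measure.

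Two further consequences follow.

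- If recording really stops at first success, the loss is not captured and cannot be found later. Applications delivered afterwards also drop out of the secondary endpoints.
- The plan expects that conduction may return, and it schedules a visit to look for it. Yet the result enters no listed endpoint and none of the described analyses (baseline summaries, Kaplan-Meier medians, log-rank test, Cox model). Repeat-ablation data could be pooled into index-procedure totals, because the plan does not say where they are to be included.

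At stake are both primary endpoints and the planning values passed to the next trial.

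**Working it through.** **Inputs.** From Sample Size Justification: 15 patients per arm, 15 + 15 = 30, which agrees with the stated total. The plan gives no power calculation to reproduce. It also gives no reversion rate, no time to success and no time to regain block, so every such value below is an assumption.

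**1. Following one patient through the rules.** Block appears at time t, is lost, and is not regained before the procedure stops at time s. The endpoint definition is met at t. The censoring rule does not apply, because success was reached. The patient is an event at t. Under an end-of-procedure rule the same patient is censored at s and is not a success.

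**2. Success proportion.** Each such patient moves an arm by 1/15 = 6.7 points: 15/15 = 100%, 14/15 = 93.3%, 13/15 = 86.7%, 12/15 = 80.0%.

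**3. Chance that the situation arises.** P(at least one reversion in an arm of 15) = 1 − (1 − r)^15. For r = 2%, 5%, 10% and 20% this is 26%, 54%, 79% and 97%.

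**4. Block lost, then regained.** Simulated arms of 15 (400,000 per setting). First times are exponential with mean 1. Each patient reverts with probability r and then needs an extra exponential time with mean q. The table shows the rise in the average arm median when the final rhythm is timed instead of the first and, in brackets, the share of arms whose median is unchanged.

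| r | q = 1 | q = 0.5 | q = 0.25 |
|---|---|---|---|
| 2% | 2.0% (89%) | 1.4% (91%) | 0.8% (94%) |
| 5% | 5% (75%) | 3% (80%) | 2% (85%) |
| 10% | 11% (55%) | 7% (63%) | 4% (73%) |
| 20% | 22% (29%) | 14% (39%) | 8% (52%) |

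For scale, the sampling SD of a 15-patient median is 36% of its mean in this model.

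The size also depends on when the clock starts. The endpoint list starts it at energy application; Statistical Analyses starts it when the ablation procedure begins, which may include mapping. Suppose a fixed lead-in equal to the mean ablation time (1) is inside the clock. The average first-onset median is then 0.725 + 1 = 1.725, so each shift is multiplied by 0.725/1.725 = 0.42. At q = 1, shifts of 5.2%, 10.6% and 22.4% become about 2%, 4% and 9%.

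**5. Block lost and never regained, given that it happens to k of 15.** With censoring at procedure stop, the average Kaplan-Meier median is longer by about 10% (k = 1), 20–24% (k = 2) and 31–41% (k = 3). The ranges cover different assumed stopping times. The median is unchanged in about 47%, 21% and 8% of arms. These figures are conditional on k; they are not expected effects.

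**6. Applications missed if recording stops at first success.** If k of 15 patients need a further applications and the mean up to first success is b, the understatement is ka/(15b + ka). For k = 1, a = 2, b = 10 it is 2/152 = 1.3%. For k = 4, a = 2, b = 3 it is 8/53 = 15.1%.

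**7. What a day-30 endpoint could show.** 15/15 against 11/15 gives a two-sided Fisher p of 0.0996. Power of that test at 0.05 for an assumed 95% against 80% is 8%.

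**The case against.** The strongest reply is that the plan already has a default. A Kaplan-Meier event is conventionally the first occurrence, the endpoint is called acute, and censoring is limited to patients who never reach it. All of this points to first onset, which is a legitimate choice. This stands against any suggestion that the event is wholly undefined. It does not remove the problem, because that default is exactly what scores a patient who ends the procedure conducting as a success.

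A reader might also infer that Research Design contradicts itself, since it also says "Data will be collected prospectively (perioperatively and at follow up visit"). The documents do not support that. The narrower sentence closes a paragraph about the ablation and can be confined to intraprocedural data, with the other sentence as the general overview. What remains is that, taken literally, stopping at success fits poorly with procedure time and with applications that can run past it. The listing of procedure time may itself show that whole-procedure recording was intended.

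On day 30, the secondary endpoint list is not presented as exhaustive, the trial is a 30-patient pilot aimed at time to success, and the comparison would have little power. These are good reasons to keep the endpoint descriptive. They are not reasons to leave a planned assessment without a stated use.

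Finally, the sizes are all assumed, and many are small. That is correct and limits the verdict.

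Status at procedure end also depends on when the operator stops, and the envelope reveals the catheter. Any observation period therefore has to be fixed in advance and be common to both arms.

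**Conclusion.** The concern holds on the text. Read literally, block that is reached, lost and not regained is an acute success. Recording to success could miss the loss and truncate secondary endpoints. The day-30 result has no listed use, and repeat-ablation data have no stated place. The plan should be changed on these points.

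The size cannot be taken from the documents. One patient is worth 6.7 points of an arm's success proportion. For block lost and regained, the average median shifts by about 1% to 22%, depending on the assumed reversion rate (2% to 20%) and time to regain block, and by less with mapping inside the clock. All of these shifts lie below the sampling SD of the median. The exponential model is itself an assumption.

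A reader might go further and infer that the comparison is biased towards one catheter, or that the medians will certainly move. The documents support neither: they suggest no difference in reversion between arms, and in many simulated arms the median does not change.

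**What to change.** 1. Count acute success only if junctional rhythm or complete heart block is present at the end of the index procedure, timed at the onset of that final rhythm. Censor patients who lose it and do not regain it at procedure stop, as the plan already does for non-success. Report time to first onset as a sensitivity analysis. The investigators set any observation period in advance, the same in both arms.
2. Record to the end of the index procedure in every patient, and measure all four secondary endpoints over it.
3. Keep repeat-ablation data out of the index-procedure analyses and list them separately by arm.
4. Add one descriptive secondary endpoint by arm among all randomised patients, with an exact 95% CI: acute success, no returned conduction at the existing day-30 visit, and no earlier repeat ablation. Patients without acute success count as failures. Show missed visits by best- and worst-case bounds; for example, 11 successes, 3 failures and 1 missed visit give 11/15 = 73% to 12/15 = 80%. Report deaths before the visit separately, not as possible successes.

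The cost is a few sentences and recording to procedure end; no visit, procedure or patient is added. Some times will lengthen, acute success may be slightly lower, and the day-30 comparison will be imprecise at 15 per arm.

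### The catheter is revealed at consent with no rule that the operator is named first, so if several operators take part and cases move afterwards, an operator difference can appear as a catheter effect.

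*Combined protocol and SAP*

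**What the plan says.** **Timing of the reveal.** Under Research Design, "Patients will be recruited in the Cardiology Clinics of our institution and will be screened by Cardiology Research Staff". After written consent, "subjects will be randomized by random computer programming to receive an ablation with MIFI technology or standard ablation catheter for their procedure". The Sample Size Justification section gives the mechanics: "Once a patient has consented to participate, the next envelope will be opened for that patient and the catheter assignment will be revealed".

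**Restrictions on the randomisation.** There are 30 patients, 15 per arm. The only restriction is on block size: "Variable block sizes will be used to improve the blinding of the clinical team". No stratification factor is named.

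**Scheduling.** Inclusion criterion 3 reads: "Patients have already been scheduled for their standard of care ablation". It says nothing about who will perform the procedure.

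**Analysis.** "The primary analysis is the estimation of Kaplan-Meier median times to successful endpoints for each of the two study arms". A log-rank test without named strata is added. A Cox model is fitted if baseline characteristics differ between arms, and those characteristics are introduced this way: "The baseline demographic and clinical characteristics of the patients included in this study will be summarized by study arms".

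**Operators.** The document does not say how many operators there are, who ablates, or whether the operator is recorded. The first page lists a principal investigator and co-investigators, and the Additional Information section refers to physicians in the plural. Neither says who performs the ablations.

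**The concern.** Randomisation protects against differences that are fixed before the assignment is known. An operator chosen or changed after the reveal is outside that protection. A MiFi case could, for instance, be moved to the operator who knows the new catheter best, and nothing in the plan would prevent or reveal it.

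The endpoints are exposed to this. The ablation target is found by mapping and pacing during the case, so time to block plausibly depends on who holds the catheter. The same holds for procedure time, radiation time, and the number and duration of applications. The Cox adjustment offers no safeguard, because it is triggered by patient characteristics and operator is not one of them.

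The stake is the pilot's main product. Its arm-specific times are meant to inform the design of a fully powered trial, so a ratio that mixes operator with catheter would pass into that trial's assumptions.

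**Working it through.** **The plan's own figure.** 15 + 15 = 30 agrees. The plan states no alpha, power or effect size, so there is no sample-size formula to reproduce.

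**Inputs.** From the document: 15 patients per arm, a log-rank test, no strata. Everything else is assumed:
- two operators and no true catheter effect;
- log-normal times with SD 0.8 on the log scale;
- a slower operator who takes r = 1.5 or 2 times as long as the faster one;
- every case ending in success (no censoring);
- a two-sided 5% test.

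**Step 1: bias in the median ratio.** Set the faster operator's median to 1. If that operator performs a share p of an arm's cases, the arm's median m solves

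p · Φ(ln m / 0.8) + (1 − p) · Φ((ln m − ln r) / 0.8) = 0.5.

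The faster operator has share p in the MiFi arm and 1 − p in the standard arm.

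| Faster operator's share, MiFi / standard | Ratio MiFi/standard, r = 1.5 | Ratio MiFi/standard, r = 2 |
|---|---|---|
| 50 / 50 | 1.00 | 1.00 |
| 67 / 33 | 1.143/1.312 = 0.87 | 1.252/1.598 = 0.78 |
| 80 / 20 | 1.083/1.385 = 0.78 | 1.139/1.755 = 0.65 |
| 100 / 0 | 1/1.5 = 0.67 | 1/2 = 0.50 |
| One operator only | 1.00 | 1.00 |

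Starting from an even split, 80/20 means moving on average 15 × (0.80 − 0.50) = 4.5 cases per arm, or 9 of 30. The 67/33 row needs 15 × (0.667 − 0.50) = 2.5 per arm, or 5 of 30.

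**Step 2: false-positive rate of the log-rank test.** This was simulated with 15 per arm. Operators are named evenly before the reveal, and cases are then switched to reach 80/20.

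| Log-rank test | r = 1.5 | r = 2 |
|---|---|---|
| Unstratified, no switching | about 6% | about 6% |
| Unstratified, switched to 80/20 | about 13% | about 25% |
| Stratified by the operator named beforehand | 12–13% | about 24% |
| Stratified by the operator who performed the case | 5–6% | 5–6% |

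Stratifying by the named operator fails because that operator was fixed before the assignment and is unrelated to arm. In this scenario, among patients first booked with the faster operator, all MiFi cases but only 40% of standard cases stay with that operator. Among those booked with the slower one, 60% of MiFi and none of the standard cases move to the faster operator. The imbalance therefore persists inside each stratum.

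**Step 3: sensitivity to the distribution.** With exponential times and operator hazard ratios of 1.5 and 2, an 80/20 split gives standard/MiFi median ratios of 1.28 and 1.53, that is MiFi/standard 1/1.28 = 0.78 and 1/1.53 = 0.65. The unstratified log-rank test rejects in 10.5% and 19.1% of trials.

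**Step 4: chance imbalance, kept separate.** If each of two operators happens to do 15 of the 30 cases independently of arm, a 10:5 or worse split of an operator's cases between arms has hypergeometric probability 0.143. This produces no average bias, and the rejection rate stays near 6%. It is not evidence for the mechanism above.

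**The case against.** The strongest counter-text is inclusion criterion 3. The procedure is booked before enrolment, so where the booking names an operator, steering would mean changing an existing appointment rather than making a first assignment. This stands and makes the gap narrower. It does not close it, because the criterion neither names an operator nor bars a change after the reveal.

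Second, this is one division at one site with 30 patients, and a single operator may do every case. The point is then moot. The plan does not say so, and neither the co-investigator line nor the plural physicians settles it.

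Third, the magnitudes rest on assumed speed ratios and splits, and 80/20 takes a good deal of switching. That also stands; the figures show what could happen, not what is expected.

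Fourth, the plan says the envelope procedure keeps the clinical team blinded. It gives no mechanism for withholding the catheter from whoever books or performs the case.

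Fifth, this is a pilot whose primary aim is estimation, with the log-rank test as an addition. That lowers the weight of the rejection rates, but not of the median ratios, which are what the pilot is for.

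A reader might infer that operators will be chosen by catheter, or that leaving operator out of the randomisation biases the comparison by itself. The documents support neither. They show no intention to steer cases, and without a link between operator and arm there is only chance imbalance.

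**Conclusion.** The concern holds as a conditional one. The catheter is revealed at consent, no text fixes or records the operator, and operator enters neither randomisation nor analysis. Bias requires three things the documents leave open: more than one operator, a material difference in speed between them, and cases moved after the reveal.

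If all three occur at the assumed 80/20 split, a null catheter effect would show as a median about 22% shorter on MiFi at a 1.5-fold operator difference (1 − 0.78) and about 35% shorter at a 2-fold difference (1 − 0.65). Remove any one of them and the systematic effect is zero. This is a cheap safeguard worth adding to a short pilot plan, not a flaw that invalidates the design.

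**What to change.** In the Sample Size Justification section, where the envelopes are described:

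- Require the research staff to write the scheduled operator on the randomisation form before the envelope is opened, and keep that operator unless a change is unavoidable.
- Record the operator who actually performed the case, and any change with its reason.

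In the Statistical Analyses section:

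- Tabulate planned and actual operator by arm.
- If more than one operator took part, add a sensitivity log-rank and Cox analysis stratified by the actual operator. Do not stratify by the planned operator for this purpose, since that leaves the bias almost untouched.
- State that the stratified analysis has no information if operator and catheter coincide completely. Only naming the operator in advance protects against that case.

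If one operator will do every ablation, a sentence saying so replaces all of this.

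The cost is one form field, a short protocol addition and one extra analysis. The small practical burden is that the operator must be named before the envelope is opened; the procedure itself is already scheduled by then.

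### The plan claims blinding of the clinical team from steps that can only conceal upcoming assignments, and does not say when, relative to the procedure, the envelope is opened

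*Combined protocol and SAP*

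**What the plan says.** All references are to the combined protocol and SAP.

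- **Sample Size Justification, on blocks:** "Variable block sizes will be used to improve the blinding of the clinical team". The block sizes are not given.
- **Sample Size Justification, on envelopes:** the project biostatistician and team prepare them. "Once a patient has consented to participate, the next envelope will be opened for that patient", at which point "the catheter assignment will be revealed. This will maintain the blinding of" the clinical team.
- **Research Design:** "After providing written informed consent, subjects will be randomized by random computer programming". Also, "Patients will be recruited in the Cardiology Clinics of our institution".
- **Inclusion Criterion, item 3:** "Patients have already been scheduled for their standard of care ablation".
- **Introduction, on the test device:** "A novel catheter with three mini electrodes within the ablation tip", which gives additional bipolar signals beside the usual distal and proximal recordings.
- **Study Aims, on the comparator:** "the standard bipolar catheter will be 8mm non-irrigated, and from the following list" of three products.
- **Statistical Analyses:** the clock starts when the procedure begins. Patients without success are censored when it is stopped.

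No section says who opens the envelope, where, or how long before the procedure. None says whether the envelopes are sealed, opaque or numbered. None describes a masked operator, endpoint assessor or analyst.

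**The concern.** Two separate matters are involved.

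The first is a statement that cannot be true as written. Blinding means that people do not know the arm after assignment; concealment means that they cannot know it before. The plan describes tools for concealment and claims blinding for them, twice. The pilot is meant to supply the inputs for a full-size randomised trial. Whoever designs that trial needs to know that the time-to-success estimates came from operators who knew the arm.

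The second is timing. If consent is signed at a clinic visit and the envelope opened then, the arm is known during the wait for the procedure. A cancellation or postponement could then depend on the arm, and so could the choice among the three listed control catheters. A patient lost in that interval has been randomised but has no starting point for the primary analysis, and the plan does not say how such a patient is reported.

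**Working it through.** The plan gives no figure for blinding or loss to reproduce. Its one relevant figure is the allocation: 15 + 15 = 30, which agrees with the stated total.

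**Step 1. What variable blocks can do.** Suppose the block size is fixed and known, and all past assignments are known. With a permuted block of size 2m in 1:1 allocation, the expected share of assignments that are certain before they are made is 1/(m + 1). The block sizes below are assumptions, since the plan gives none.

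| Block size | m | Share certain in advance |
|---|---|---|
| 2 | 1 | 1/2 = 50.0% |
| 4 | 2 | 1/3 = 33.3% |
| 6 | 3 | 1/4 = 25.0% |

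Varying the block size works against this kind of prediction. Its effect is wholly on assignments not yet made. Once an envelope is open, that patient's arm is known whatever the block size. The prediction also requires knowledge of past assignments, so the precaution matters most when the team is not blinded.

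**Step 2. Can the team be blind after opening?** The envelope reveals the catheter. The operator handles it, and the mini-electrode signals, which are the rationale for the test device, come from one arm's catheter only. With no masked role described anywhere, there is nobody to whom the blinding claim can be shown to apply.

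**Step 3. When is the arm known?** Research Design and Sample Size Justification both tie assignment to consent and to nothing else. Clinic recruitment and an already scheduled ablation make an interval between consent and procedure possible. They do not establish one: neither the interval nor the place of opening is stated, and same-day consent and opening also fits the text.

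**Step 4. What happens to a patient whose procedure never starts?** Statistical Analyses provides two outcomes: success, or censoring when the procedure is stopped. Both need a procedure that began. A randomised patient without one falls into neither category.

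**Step 5. Size.** Each such patient is 1/15 = 6.7% of an arm; two are 2/15 = 13.3% and three are 3/15 = 20.0%. These are shares per event, not expected losses. The documents give no loss rate and no distribution of times, so no bias in minutes can be derived.

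**The case against.** The strongest reply is that this is a slip of vocabulary. Envelopes prepared by a biostatistician, variable blocks and opening after consent form a recognisable concealment procedure, and the authors probably meant that. No planned analysis relies on blinding: the Kaplan-Meier medians, log-rank test and Cox model would be identical if the word were corrected. Randomising after consent is also ordinary practice. This largely stands, and it limits the weight of the point. It does not rescue the sentences, which assert a property the design lacks. Nor does it settle the opening point, which remains unstated.

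A second reply concerns the control catheter. The choice arises only for control patients and stays within the defined list, and nothing suggests that it depends on expected outcome. That stands, so recording the intended control catheter in advance is optional.

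A third reply is that calling the procedure concealment would itself be an unsupported assurance unless the envelopes are specified. That stands too, and the fix includes the specification.

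A reader might go further in three ways that the documents do not support:

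- **That the arm is known days ahead.** The consent-to-procedure interval is not given.
- **That the time or success results are biased by a computable amount.** No input for that exists. The success endpoint is a rhythm, either heart block or a junctional rhythm, which limits biased ascertainment of success.
- **That unblinded operators stop at different times by arm.** The documents give no basis for this claim, and later opening would not change operator influence during the case.

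**Conclusion.** The blinding statements are wrong as written and should be corrected. That conclusion needs no assumption beyond the text: the catheter is revealed, the devices differ, and no masked role is described. If clinical team were meant to exclude the operator, some blinding would be conceivable, but the plan describes no such separation.

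The timing part is conditional. It has force if consent precedes the procedure day, because the arm is then known while cancellation is still possible. If consent and opening are on the same day, moving the opening gains little. The only size available is 6.7% of an arm for each randomised patient whose procedure does not start; the frequency and effect of such losses cannot be obtained from the documents. Overall this is a change that should be made at modest cost. It does not show that the comparison is invalid.

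**What to change.** 1. Replace both blinding statements with: *Variable blocks and sequentially numbered, sealed, opaque envelopes are used to conceal upcoming assignments; the operator and procedure team are not blinded.*
2. State the opening point: in the lab, after eligibility is reconfirmed and before the procedure begins. This precedes both clocks in the plan, namely procedure start in Statistical Analyses and radiofrequency application under Primary endpoints. It also precedes mapping.
3. Name the role that opens the envelope.
4. Report by arm any randomised patient whose procedure did not start.
5. Optional: before opening, record which listed standard catheter would be used if the patient is assigned to control.

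The cost is two reworded sentences, one or two added sentences, the envelope safeguards, an eligibility recheck in the lab and one by-arm count; the optional item adds a line to the data sheet. The practical downside is that both catheter types must be on hand for each case and the patient learns the arm later. Study Aims says the catheters are already in use at the site. The Product section says purchasing follows standard of care but not whether it is per patient, so the site should confirm that stocking both is workable. If it is not, items 1, 3 and 4 still apply, and the actual opening point should still be stated.
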